5.1. Inclusion Criteria

Each potential participant must satisfy all of the following criteria to be enrolled in the study:

- 1. completed the maintenance phase (Week 32) of Study TRD3013 and had esketamine nasal spray in combination with continuing SSRI/SNRI administered through Week 30 (every 2 week dosing) or Week 31 (once weekly dosing) of Study TRD3013, and continues to be willing to be treated with esketamine nasal spray.
- 2. must, in the opinion of the investigator, be benefiting from continuation of esketamine nasal spray in combination with their current SSRI/SNRI based on efficacy and tolerability assessed on Day 1 of this study.
- 3. must be medically stable based on the investigator's judgment.
- 4. must sign an ICF indicating that he or she understands the purpose of, and procedures required for, the study and is willing to participate in the study.
- 5. a woman of childbearing potential must have a negative urine pregnancy test on Day 1.
- 6. a woman must be (as defined in Appendix 2, Contraceptive and Barrier Guidance)
 - a. Not of childbearing potential
 - b. Of childbearing potential and
 - Practicing a highly effective, preferably user-independent method of contraception (failure rate of <1% per year when used consistently and correctly) and agrees to remain on a highly effective method while receiving study intervention and until at least 6 weeks after last dose the end of relevant systemic exposure. The investigator should evaluate the potential for contraceptive method failure (eg, noncompliance, recently initiated) in relationship to the first dose of study intervention. Examples of highly effective methods of contraception are located in Appendix 2, Contraceptive and Barrier.
- 7. male participants who are sexually active with a woman of childbearing potential must agree to the following during the intervention period and for at least 1 spermatogenesis cycle (defined as approximately 90 days) after receiving the last dose of study intervention (ie, esketamine nasal spray), must fulfill the following criteria:
 - must be practicing a highly effective method of contraception with his female partner.
 - must use a condom if his partner is pregnant.
 - must agree not to donate sperm.

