7.2. Participant Discontinuation/Withdrawal From the Study

A participant will be withdrawn from the study for any of the following reasons:

- The participant discontinues study intervention (see Section 7.1)
- Esketamine nasal spray becomes accessible in an individual's local country
- Lost to follow-up
- Withdrawal of consent
- Death

When a participant withdraws before study completion, the reason for withdrawal is to be documented in the eCRF and in the source document. If the reason for withdrawal from the study is withdrawal of consent then no additional assessments are allowed.

Refer to Section 4.4 for study completion definition for participants.

Withdrawal of Consent

If a participant is unable to return for scheduled visits, it does not necessarily constitute withdrawal of consent. Alternate follow-up mechanisms that the participant agreed to when signing the consent form apply, as local regulations permit.

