Study participation will continue for up to a maximum of 2 years (104 weeks), or until esketamine nasal spray becomes accessible in the participant's local country, whichever occurs first. Participants will have access to esketamine nasal spray for a maximum of 2 years during this study. If esketamine nasal spray becomes accessible locally before the 2-year endpoint, then participants will be considered as having completed the open-label extension study and will be switched to a commercially available supply if in the opinion of the treating physician, the participant continues to benefit from treatment and the participant wishes to continue the esketamine nasal spray treatment. Once esketamine nasal spray becomes accessible in a given country, all participants in the long-term extension study will be discontinued at all sites in that country. Study site personnel will notify participants of study termination and schedule an end-of-study visit with each participant.

Randomization

Since this is an open-label extension to Study 54135419TRD3013, no randomization is performed.

Informed consent may be obtained from participants at any time in the 4 weeks before Day 1 (ie, at or after Week 28 visit in Study 54135419TRD3013). Day 1 of this study will be the day of the first esketamine nasal spray dose or Day 1 will be the date of informed consent.

CONFIDENTIAL – FOIA Exemptions Apply in U.S.

Treatment exposure

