5.4. Secondary Endpoint(s) Analysis

5.4.1. Relapse

5.4.1.1. Definition

A participant is defined as a remitter at a given time point if the MADRS total score is ≤ 10 at that time point.

A relapse is defined by any of the following:

- a) Worsening of depressive symptoms as indicated by MADRS total score ≥22 confirmed by 1 additional assessment of MADRS total score ≥22 within the next 5 to 31 days. The date of the second MADRS assessment will be used for the date of relapse.
- b) Any psychiatric hospitalization for
 - a. worsening of depression
 - b. suicide prevention or due to a suicide attempt

For any of these events, the start date of hospitalization will be used for the date of relapse.

c) Suicide attempt, completed suicide, or any other clinically relevant event determined per the investigator's clinical judgment to be indicative of a relapse of depressive illness, but for which the participant was not hospitalized. The onset of the event will be used for the date of relapse.

In case more than 1 of the relapse criteria are met, the earliest date will be defined as the date of relapse for that participant.

The secondary endpoint is no relapse until the end of the prospective observation period at Week 104 visit (or end-of-study) visit, and no discontinuation of (any component of) study intervention within group of subjects who are in remission at Week 8 visit of Study 54135419TRD3013.

To be aligned with ESCAPE-TRD study, for subjects who do not have an available MADRS result at the Week 8 visit but did not discontinue study intervention or withdraw from study before Week 8, LOCF of MADRS will be applied at Week 8.

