5.4.1.2. Analysis Methods

The efficacy analysis of data will be based on the Safety/Efficacy analysis set.

The proportion of subjects with the secondary endpoint (as defined above) will be estimated together with 95% Clopper-Pearson confidence interval. The incidence rate of subjects with the secondary endpoint (as defined above) will be estimated together with 95% confidence interval. The incidence rate is defined as the number of subjects who achieve the secondary endpoint divided by the time at risk. Time at risk is defined as time from Week 8 visit in Study 54135419TRD3013 until last visit date. The 95% confidence interval of the incidence rate will be calculated based on a Poisson model with achievement of secondary enpoint as dependent variable, an intercept and log (time at risk) as offset.

The remission time point is the first time point at which the participant is in remission. This analysis will only include participants for whom the remission time point is before or at Week 32 of Study 54135419TRD3013. Time to first relapse (from remission time point) will be analyzed by the Kaplan-Meier method. Time to relapse will be summarized with median, 25th and 75th percentile (if estimable). Confidence intervals of 25th, 50th, and 75th percentile of time to relapse will also be provided.

A frequency table of the number of relapses for subjects in remission at Week 8 of Study 54135419TRD3013 will be made. A frequency table of the number of relapses for subjects in remission at any time point during Study 54135419TRD3013 will be made. A frequency table of the number of relapses for subjects who were not in remission during Study 54135419TRD3013 but who are in remission at any time point during Study 54135419TRD4010 will be made

The relapse narratives of relapses during Study 54135419TRD4010 will be listed.

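### The relapse-free incidence rate divides successes by person-time, so it rises as follow-up shortens and can rank a worse result above a better one when follow-up differs

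*SAP*

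**What the plan says.** SAP Section 5.4.1.1 defines the outcome: "The secondary endpoint is no relapse until the end of the prospective observation period at Week 104 visit (or end-of-study) visit". It adds that no component of study intervention may have been discontinued, and it restricts the group to participants in remission at Week 8 of the parent study.

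SAP Section 5.4.1.2 reports the proportion achieving this, with a Clopper-Pearson interval, and then adds a rate: "The incidence rate is defined as the number of subjects who achieve the secondary endpoint divided by the time at risk". For the denominator, "Time at risk is defined as time from Week 8 visit in Study 54135419TRD3013 until last visit date". The interval comes from a "Poisson model with achievement of secondary enpoint as dependent variable, an intercept and log (time at risk) as offset", so success is clearly meant as the event.

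Three other provisions bear on follow-up:

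- SAP Section 1.2: "If esketamine nasal spray becomes accessible locally before the 2-year endpoint, then participants will be considered as having completed the open-label extension study". Once that happens, "all participants in the long-term extension study will be discontinued at all sites in that country".
- Protocol Section 7.2 lists, as a reason for withdrawal from the study, "The participant discontinues study intervention (see Section 7.1". Relapse as such is not listed there or in Section 7.1.
- SAP Section 5.7.8 repeats the secondary endpoint by subgroup, including four regions.

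The same section of the SAP also plans a Kaplan-Meier analysis of time to first relapse, relapse frequency tables and a listing of relapse narratives.

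**The concern.** An incidence rate makes sense for an event that has an onset and ends the time at risk. The SAP's adverse-event rate (Section 5.3.2.1.1) is of that kind: it counts participants with the event and, for them, stops the clock at first occurrence. Here the counted outcome is the absence of an event, known only when observation ends. Longer success does not add to the numerator, but it does add to the denominator, so sustained benefit lowers the rate.

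A reader will take a higher success rate per year as better and will assume that dividing by time has adjusted for unequal follow-up. It has not; dividing by time adds to the distortion. Follow-up can differ for two reasons: countries may close at different times, and participants who discontinue must leave. Region rows are where such differences would be set side by side.

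**Working it through.** **Inputs.** The SAP gives no value for this rate, so there is none to reproduce. Parent-study Week 8 to Week 32 is 24 weeks, and the extension lasts at most 104, giving 128 weeks. Success proportions, hazards and closure dates are not in the documents and are assumed. Closure at extension Week 52 gives 24 + 52 = 76 weeks. With 52.18 weeks per year, 128 weeks is 2.453 years and 76 weeks is 1.456 years. Up to two extra weeks for a safety follow-up visit are ignored.

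**Step 1: the same follow-up for everyone in a group.** Rate = success proportion / years.

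| Success | Follow-up | Rate per year |
|---|---|---|
| 100% | 128 weeks | 1/2.453 = 0.408 |
| 80% | 128 weeks | 0.8/2.453 = 0.326 |
| 80% | 76 weeks | 0.8/1.456 = 0.549 |

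The third row is worse than the first on both success and duration, yet scores higher. This does not depend on what happens after failure: the first row has no failures, and if failures in the third row left early its rate would only rise. Success of 76/128 = 59.4% over 76 weeks ties with perfect success over 128.

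**Step 2: a partly closed region, failures staying to the planned end.** Take a constant failure hazard h from extension Day 1. Success is exp(-ht), with t = 104/52.18 = 1.993 or 52/52.18 = 0.997 years, averaged over closed and open countries. Participants free of failure at closure count as successes.

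- h = 0.1, no closure: 0.819/2.453 = 0.334.
- h = 0.2, half closed at Week 52: success (0.671 + 0.819)/2 = 0.745; mean time (2.453 + 1.456)/2 = 1.955; rate 0.381.

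The region with twice the hazard scores higher.

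**Step 3: which reversals depend on failures leaving.** If every failure leaves when it occurs, mean person-time becomes 24/52.18 + (1 - success)/h. For h = 0.1 with no closure this is 0.460 + 1.807 = 2.267, and the rate is 0.361.

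| Comparison | All failures leave | All failures stay |
|---|---|---|
| h = 0.2 half closed, against h = 0.1 open | 0.430 against 0.361 | 0.381 against 0.334 |
| h = 0.3 half closed, against h = 0.1 open | 0.394 against 0.361 | 0.330 against 0.334 |
| h = 0.2 quarter closed, against h = 0.1 open | 0.369 against 0.361 | 0.321 against 0.334 |
| No closure: 75% (failures at extension Week 4) against 80% (failures at Week 78) | 0.380 against 0.340 | 0.306 against 0.326 |

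Only the first row reverses under both assumptions. With the same share of failures staying in both groups, the second reversal is gone when about 90% stay (0.336 against 0.337), the third when about 40% stay (0.348 against 0.350), and the fourth when about 60% stay. For the fourth, the weeks per participant are 103 + 25s and 122.8 + 5.2s for a staying share s, and the rates tie at s = 9.7/16.1 = 0.60.

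**Step 4: the Poisson interval at full follow-up, n = 100.** Limits are rate × exp(±1.96/√x) for x successes, shown on the proportion scale after multiplying by 2.453.

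| Successes | Poisson | Clopper-Pearson | Width ratio |
|---|---|---|---|
| 60 | 0.466 to 0.773 | 0.497 to 0.697 | 1.5 |
| 80 | 0.643 to 0.996 | 0.708 to 0.873 | 2.1 |
| 95 | 0.777 to 1.162 | 0.887 to 0.984 | 4.0 |

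At 95 successes the rate is 0.387 (0.317 to 0.474) per year, while the largest possible value is 0.408.

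**The case against.** The study is single-arm and descriptive, with no hypothesis and no planned test between subgroups. The proportion and the Kaplan-Meier analysis stand beside this rate. If follow-up is equal, the order of results is preserved. The documents give no access dates and no count of Week 8 remitters, and a region may pool several countries. All of this is correct and limits the consequence. It does not make the line interpretable.

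The status of participants at closure is also not spelled out. The definition excludes discontinuation of study intervention, and SAP Section 1.2 describes participants in a closed country both as completers and as discontinued. Counting those free of failure as successes is the natural reading, because the endpoint runs to Week 104 or end-of-study, but the closure examples rest on it.

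A reader might infer that early failures always shrink the denominator, so that misordering is likely even without country closure. The documents do not support that. Discontinuation of study intervention requires withdrawal, but relapse alone does not; the investigator decides whether the participant still benefits. The SAP clock runs to the last visit, and the SAP tabulates the number of relapses, so follow-up after relapse is possible. Three of the four comparisons in Step 3 therefore depend on how many failures leave.

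The proportion is not free of follow-up length either. With a hazard of 0.2 per year from Week 8, success is 61.2% over 128 weeks and 74.7% over 76. That calls for reporting follow-up beside it, and is no reason to keep the rate.

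**Conclusion.** The point holds. As defined, the rate rises when observation shortens and can place a worse result above a better one when follow-up differs. The clearest illustration is 0.55 per year for 80% over 76 weeks against 0.41 for 100% over 128 weeks. In a partly closed region, a hazard of 0.2 per year can score 0.381 against 0.334 for 0.1 per year with no closure, even if all failures stay. All success proportions, hazards and closure dates here are assumptions.

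The Poisson interval is a secondary defect: too wide in the cases computed, and able to include impossible values. The widths shown are for full follow-up.

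A reader might go further and infer that the regions will be misranked, or that the trial's efficacy conclusions are compromised. Neither follows. No closure dates are given, and the proportion, Kaplan-Meier analysis, frequency tables and narratives are unaffected. The effect is confined to one descriptive line and its subgroup versions. It should be fixed because it is misleading and cheap to remove.

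**What to change.** Delete the four sentences in SAP Section 5.4.1.2 that introduce the rate, define it, define its time at risk and specify its Poisson interval. Keep the proportion with its Clopper-Pearson interval, and present follow-up duration beside it, especially by region. Nothing in the protocol is lost: its objective is the proportion relapse-free (Section 3), and its planned analyses are the frequency of relapse and time to relapse (Section 9.4.3).

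If a rate is wanted, count participants with a first failure (relapse, or relapse or discontinuation) and divide by time to first failure or last visit, on the pattern of the SAP's adverse-event rate.

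An optional refinement is to start events and time at extension Day 1. Entry required esketamine "administered through Week 30 (every 2 week dosing) or Week 31 (once weekly dosing) of Study TRD3013", so with a Week 8 origin the weeks before that cannot contain a discontinuation. If failures start only in the extension at 0.2 per year, a Week 8 origin gives 0.329/(0.460 + 1.643) = 0.156 over 128 weeks and 0.181/(0.460 + 0.903) = 0.133 over 76. A Day 1 origin gives 0.20 in both. The SAP would then need to say how relapses between Week 8 and Day 1 are handled.

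The cost is one table line removed or reprogrammed, with its subgroup versions. No new data are needed.

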5.4.2. Montgomery-Asberg Depression Rating Scale (MADRS)

5.4.2.1. Definition

The MADRS is a clinician-administered scale designed to measure depression severity and detects changes due to antidepressant intervention. (Montgomery 1979) The scale consists of 10 items, each of which is scored from 0 (item not present or normal) to 6 (severe or continuous presence of the symptoms). Higher scores represent a more severe condition. The MADRS evaluates reported sadness, apparent sadness, inner tension, reduced sleep, reduced appetite, concentration difficulties, lassitude, inability to feel, pessimistic thoughts, and suicidal thoughts. The test exhibits high inter-rater reliability. The typical recall period for the MADRS is 7 days.

The MADRS total score is the sum of scores from individual question items at a given time point, and ranges from 0 to 60. Higher scores represent a more severe condition. If 2 or more items are missing, no imputation will be performed, and the total score will be left missing. Otherwise, the total score will be calculated as the sum of the items present multiplied by the ratio of the maximum possible number of items (i.e., 10) to the number of items present.

Negative changes in MADRS total score indicate improvement.

5.4.2.2. Analysis

Descriptive statistics of the actual values and the change from Study 54135419TRD3013 baseline to each postbaseline time point will be presented for MADRS total score and the individual depressive symptoms. Summaries of observed data will be presented. Mean score (+/- SE) and mean changes from baseline (+/- SE) of MADRS total score will be presented graphically over time.

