8.1. Efficacy Assessments

The sponsor will use the clinician-rated scales and PROs from Week 32 in Study TRD3013 in the database for Day 1 in this long-term extension study; these procedures do not need to be repeated for participants who return for esketamine nasal spray dosing within 14 days after the Week 32 visit in TRD3013.

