5.3.3.1. Analysis Methods

5.3.3.1.1. Primary Analysis

Shift from the baseline visit in Study 54135419TRD3013 to the maximum postbaseline score pertaining to suicidal ideation or suicidal behavior (i.e., scores 1 to 10) will be summarized.

The maximum score (of scores 1 to 10) assigned to each participant will be grouped into one of three broad categories: No suicidal ideation or behavior (0), Suicidal ideation (1-5), Suicidal behavior (6-10). Participants with only a score of 11, ie. no scores between 1 to 10, will be classified a No suicidal ideation or behavior. Shifts from the baseline visit in Study 54135419TRD3013 to the maximum postbaseline category will be summarized.

A frequency distribution of the scores for the 11 categories and the 3 composite endpoints will be provided at each time point.

For the suicidal ideation score the shift from baseline visit in the 54135419TRD3013 study to the maximum during treatment will be summarized.

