5.4.5.2. Analysis

Descriptive statistics of the actual values and the change from Study 54135419TRD3013 baseline will be presented for observed case data.

Mean score (+/- SE) and mean changes from baseline (+/- SE) will be presented graphically over time.

A frequency distribution over time of the CGI-S scores at each scheduled visit will be provided for observed case data.

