5.4.6.2. Analysis

Descriptive statistics of the actual values and the change from Study 54135419TRD3013 baseline to each postbaseline time point will be presented for PHQ-9 total score for observed case data. Mean total score (+/- SE) and mean changes from baseline (+/- SE) will be presented graphically over time.

Frequency distributions of the responses to the question "How difficult have these problems made it for you to do your work, take care of things at home, or get along with other people" will be provided at each assessment time point for observed case data.

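### Apart from oral-antidepressant switchers, every scale change and C-SSRS shift starts at the parent-study baseline, so none measures within-person change during the extension

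*SAP*

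**What the plan says.** **Scale scores.** For MADRS, SAP 5.4.2.2 plans summaries of the actual values, and "the change from Study 54135419TRD3013 baseline to each postbaseline time point will be presented for MADRS total score". It also states "Mean score (+/- SE) and mean changes from baseline (+/- SE) of MADRS total score will be presented graphically over time". For CGI-S, SAP 5.4.5.2 has "Descriptive statistics of the actual values and the change from Study 54135419TRD3013 baseline will be presented for observed case data". For PHQ-9, SAP 5.4.6.2 uses the "change from Study 54135419TRD3013 baseline to each postbaseline time point will be presented for PHQ-9 total score for observed case data". SAP 5.4.9.2 does the same for the EQ-5D-5L index, EQ-VAS and sum score. This follows Protocol sections 3 and 9.4.1, which define the scale endpoints as change from TRD3013 baseline.

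**C-SSRS.** This is one of the two primary endpoints (SAP 5.3.1). The primary analysis is "Shift from the baseline visit in Study 54135419TRD3013 to the maximum postbaseline score" (SAP 5.3.3.1.1), and SAP 5.3 says the primary analysis uses safety data from both studies. SAP 5.3.3.1.3 plans no supplementary C-SSRS analysis. For adverse events, the other primary endpoint, SAP 5.3.2.1.3 does plan a version restricted to events starting at or after the first extension dose.

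**Day 1 values.** Protocol 8.1 states "The sponsor will use the clinician-rated scales and PROs from Week 32 in Study TRD3013 in the database for Day 1". Footnote a of the Schedule of Activities (Protocol 1.3) extends this to the safety assessments.

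**The exception.** SAP 5.5 takes MADRS and CGI-S changes from the switch visit in participants who change oral antidepressant during the extension.

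**The concern.** Participants enter the extension only if they completed 32 weeks and the investigator judges them to be benefiting on Day 1 (Protocol 5.1). Their change from TRD3013 baseline is therefore likely to be large before the extension begins. Every later change from that baseline adds the parent-study gain to whatever happens in the following two years.

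The primary objective concerns people who have already completed 32 weeks. A reader will want to know how scores moved after that point and whether suicidality appeared or returned. Outside the switchers, no planned output answers this within person. For the C-SSRS, a maximum taken over both studies cannot say in which study a score arose.

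**Working it through.** The plan has no hypothesis and no sample size calculation, so there is no figure to reproduce. The documents give no MADRS means or SDs, so all MADRS and C-SSRS values below are assumptions.

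**1. Reference points.** By-visit changes in SAP 5.4.2.2, 5.4.5.2, 5.4.6.2 and 5.4.9.2 use TRD3013 baseline. So do percentage-based response (5.4.3.1 for MADRS, 5.4.7.1 for PHQ-9) and all C-SSRS shifts (5.3.3 and 5.3.3.1.1). Only SAP 5.5 uses a reference visit inside the extension, for switchers.

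**2. Same participants at both visits.** Assume MADRS means of 31 at TRD3013 baseline, 8 on Day 1 and 14 later.
- Planned change on Day 1: 8 - 31 = -23.
- Planned change later: 14 - 31 = -17.
- Difference: -17 - (-23) = +6, which equals 14 - 8.

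Mean worsening can be read from the planned tables. The SD and confidence interval of the paired change, and the number of people who worsened, cannot.

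**3. Response and relapse thresholds.** Take baseline 28, 31 or 34, Day 1 score 6, 8 or 10, and worsening of 4, 6 or 8 points, giving 27 cases. In 20 the participant still counts as a MADRS responder. None reaches 22, since the highest later score is 10 + 8 = 18. In 24 the participant is no longer in remission (10 or below), which the planned per-visit remission table would show.

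**4. Different participants at the two visits.** Assume everyone starts at 31. On Day 1 half score 6 and half 14. Everyone worsens by 4, and the second half has left by the later visit.

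| Output | Day 1 | Later visit |
|---|---|---|
| Mean score | (6 + 14)/2 = 10 | 6 + 4 = 10 |
| Mean change from TRD3013 baseline | 10 - 31 = -21 | 10 - 31 = -21 |
| Response | 100% (14 is a 17/31 = 55% improvement) | 100% |
| Remission | 50% | 100% |
| Relapse by MADRS (22 or more) | none | none (leavers at 14 + 4 = 18) |
| Paired change from Day 1 | not applicable | +4 |

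The MADRS summaries look flat or better although everyone worsened. The paired change shows the +4.

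**5. Those who worsen most leave.** Simulation, 2000 runs: N = 150 (within the expected 100 to 200), baseline mean 31 (SD 5), Day 1 mean 9 (SD 6), worsening mean 4 (SD 7), scores kept within the scale.

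| Dropout | Difference of the planned means | Paired change from Day 1 |
|---|---|---|
| 0% | 4.24 | 4.24 |
| 10% | 2.95 | 2.96 |
| 20% | 1.90 | 1.89 |
| 30% | 0.89 | 0.89 |
| 40% | -0.05 | -0.05 |

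Moving the reference to Day 1 does not remove this bias. It does give a direct standard error for extension change: 0.54, against 0.80 for change from TRD3013 baseline, both without dropout.

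**6. C-SSRS.** Hypothetical ideation scores:

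| Person | TRD3013 baseline | Later maximum in TRD3013 | Day 1 | Extension maximum | Planned shift | Shift from Day 1 |
|---|---|---|---|---|---|---|
| A | 2 | 0 | 0 | 2 | 2 to 2 | 0 to 2 |
| B | 2 | 2 | 0 | 0 | 2 to 2 | 0 to 0 |
| C | 0 | 2 | 0 | 2 | 0 to 2 | 0 to 2 |
| D | 0 | 2 | 0 | 0 | 0 to 2 | 0 to 0 |

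A and B share a cell in the planned table, and so do C and D. Yet ideation returned in the extension only for A and C.

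**The case against.** The best reply is that the plan already shows deterioration in ways that do not depend on the parent baseline:
- actual values and graphs of mean score by visit;
- MADRS and PHQ-9 remission by absolute cut-off (SAP 5.4.4.2 and 5.4.8.2);
- for CGI-S, "A frequency distribution over time of the CGI-S scores at each scheduled visit will be provided for observed case data";
- relapse by an absolute MADRS threshold or clinical event, with narratives of extension relapses listed (SAP 5.4.1);
- C-SSRS frequencies at each time point;
- suicidality adverse events restricted to the extension (SAP 5.3.2.1.3).

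Protocol 4.3 makes relapse the basis for evaluating efficacy. TRD3013 baseline is the pre-esketamine reference, so the SAP does what the protocol prescribes. Also, Protocol 5.2 excludes anyone answering yes to C-SSRS ideation items 4 or 5 at Week 32. A 4 or 5 in a per-visit extension table is therefore a rise since Day 1 for any participant who met that criterion.

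Much of this stands. A reader might infer that the plan hides any worsening in the extension. The documents do not support that: step 2 shows a mean worsening in plain view, and most cases in step 3 leave remission.

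Three parts of the reply do not close the gap. Comparing by-visit means works only if the same people are at both visits. Participants who stop benefiting are discontinued, and whole countries leave when the product becomes accessible (Protocol 4.1). The relapse endpoint covers Week 8 remitters with time at risk from parent Week 8, and the Kaplan-Meier clock starts at first remission in TRD3013 (SAP 5.4.1), so both mix the two periods. C-SSRS frequencies count scores at a visit without linking them to the same person's Day 1 score.

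**Conclusion.** The gap is real but limited. Outside the switchers, no planned output gives within-person score change during the extension, its uncertainty, or the number who worsened. For a primary endpoint, the C-SSRS shift cannot separate suicidality that emerges or re-emerges after Day 1, at or below an earlier score, from suicidality confined to the parent study. The SAP gives no reason for planning an extension-only analysis for adverse events but none for the C-SSRS.

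The study is descriptive, and no test, sample size, adverse event result or relapse result changes. The addition should be made, but it does not block the analysis. The size in real data is unknown: the 4-point and 6-point illustrations rest on assumed MADRS values.

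A reader might also infer that change from Day 1 would establish that benefit is maintained. It would not. Under the assumed selective dropout in step 5, a true mean worsening of about 4 points disappears at 40% dropout with either reference.

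**What to change.** Keep all planned tables and add the following.

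- **SAP 5.3.3.1.3:** in place of no supplementary analysis, add a C-SSRS shift from TRD4010 Day 1 (the TRD3013 Week 32 value) to the maximum score during TRD4010, parallel to the extension-only adverse event analysis in 5.3.2.1.3.
- **SAP 5.4.2.2, 5.4.5.2, 5.4.6.2 and 5.4.9.2:** add paired change from Day 1 at each visit, with n and 95% confidence interval, for MADRS, CGI-S, PHQ-9, EQ-5D index and EQ-VAS.
- **Wording beside these tables:** state that they are observed-case results in participants still on treatment and do not correct for discontinuation of those no longer benefiting. Limit any statement about maintenance accordingly.

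The cost is SAP wording and a few repeat table runs with a second reference. No new data are needed, and nothing conflicts with the protocol.
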